**20.1.2 Disposition****20.1.2.1 Subject discontinuation**

Reasons for subject discontinuation from trial/IMP as specified in the End-of-Trial/Treatment Completer pages of the eCRF will be used.

**20.1.2.2 Protocol deviations**

Protocol deviations are based on the analysis dataset ADDV. Key and major protocol deviations are retrieved from the respective Study Data Tabulation Model ([SDTM] dataset (SDTM.DV.DVCAT). No further protocol deviations are programmed in the analysis datasets for ADDV (if not otherwise specified in the SAP).

**20.1.3 Demographics and other baseline characteristics****20.1.3.1 Subject demographics****Derivation of age**

Age as provided in SDTM.DM.AGE will be used.

**Derivation of BMI:**

BMI is calculated to 1 decimal place using the following formula:

$$\text{BMI [KG/M}^2\text{]} = \text{WEIGHT [KG]} / \text{HEIGHT}^2\text{[M]}$$

**Derivation of race:**

If for race more than 1 entry per subject is documented, a category “multiple” will be created.

**20.1.3.2 Other baseline characteristics**

Not applicable.

**20.1.3.3 Medical history**

For CRPS history, time since precipitating event, duration (time since onset of symptoms), and time since diagnosis are derived. If the corresponding date reported in the eCRF is incomplete, e.g., missing day or month (year is mandatory), then the missing day or month will be imputed. Missing dates will be imputed conservatively, i.e., missing values will be imputed in such a way that the imputed date leads to the longest possible time since event. Missing months will be imputed by the first calendar month of the year, and missing days will be imputed by the first calendar day of the (imputed) month.

Examples:

Missing date	Imputed date
2016-Mar	2016-Mar-01
2016	2016-Jan-01

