## 8.2 Definitions

### 8.2.1 Definition of subgroups

Two subgroups will be defined based on the duration of CRPS:

1. Subjects with duration  $\leq 2$  year from onset of symptoms suggestive of CRPS.
2. Subjects with duration  $>$  year from onset of symptoms suggestive of CRPS.

When subgroup analyses are specified, the analysis will be performed separately in each of the subgroups and overall.

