### **11.3.3 Complex regional pain syndrome history**

All CRPS history data will be presented in a subject data listing.

The CRPS history will be descriptively summarized. Time since precipitating event, duration (time since onset of symptoms), and time since diagnosis will be calculated based on the date of Visit 1 and the corresponding CRPS-related dates reported in the eCRF, and will be summarized as continuous variables. Time will be displayed in years. The CRPS etiology (precipitating event), CRPS location, previous CRPS history, and imaging methods used to support prior diagnosis (or exclude other diagnoses) will be categorically summarized.

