### 13.2 Secondary endpoints

All secondary efficacy endpoints will be analyzed for the FAS and additionally for the TCS.

The following secondary efficacy endpoints will be analyzed overall and by subgroups:

- Change from baseline to Week 12 and Week 26 in the current pain intensity score, using a numerical rating scale (NRS).
- Response to treatment, defined as at least 30%, at least 50% and at least 2 points on the NRS decrease from baseline in the current pain intensity score, at Week 12 and Week 26.
- Patient Global Impression of Change (PGIC) at Week 12 and Week 26.
- Change from baseline to Week 12 and Week 26 in the Pain Interference score of the Brief Pain Inventory (BPI).

Since this is a single-arm trial, no hypothesis testing of secondary efficacy endpoints between treatment arms is planned. All secondary efficacy endpoints will be analyzed descriptively.

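### Imputing partial CRPS onset dates to the earliest calendar day can only move subjects from the subgroup at 2 years or less to the longer one, and can date onset before a recorded injury

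*SAP*

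**What the plan says.** SAP 20.1.3.3 covers three CRPS dates: precipitating event, symptom onset and diagnosis. Only the year must be recorded: "missing day or month (year is mandatory), then the missing day or month will be imputed". The direction is fixed so that "missing values will be imputed in such a way that the imputed date leads to the longest possible time since event". In detail, the rule for a month that is not known reads "Missing months will be imputed by the first calendar month of the year"; an unknown day is set to the 1st. Each date is completed on its own. There is no floor at the injury date and no check that the three dates are in order.

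SAP 11.3.3 gives the reference point: "Time since precipitating event, duration (time since onset of symptoms), and time since diagnosis will be calculated based on the date of Visit 1".

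SAP 8.2.1 defines two subgroups by CRPS duration from onset, the first at 2 years or less, and says "When subgroup analyses are specified, the analysis will be performed separately in each of the subgroups and overall". In the current text the second subgroup carries no number after the greater-than sign. SAP 13.2 applies the split: "The following secondary efficacy endpoints will be analyzed overall and by subgroups". Those endpoints are analysed in the FAS and also in the TCS.

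The change table in SAP 7.3 shows that the subgroups came in with amendment 01. It lists no change to 20.1.3.3, and SAP 19.2 says that all changes are recorded there.

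**The concern.** Before the amendment, the imputed duration fed only a descriptive history table, where choosing the longest possible value is harmless if it is stated. The amendment gave the same variable a second use, as the basis for a cut at 2 years. For a two-way split, longest is not a neutral choice: it settles every uncertain case near the boundary in the same direction.

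The rule also sets aside information already held. Protocol 12.2.3.1 and footnote d of the schedule of events require the date of the precipitating event, and also the onset and diagnosis dates. An onset set to 1 January can then precede an injury whose exact date is on file. A reader of the subgroup tables would see some short-duration subjects reported as long-duration, with nothing to mark them.

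**Working it through.** **Inputs from the documents.** Imputation rule (SAP 20.1.3.3). Duration = Visit 1 minus onset (SAP 11.3.3). Cut at 2 years (SAP 8.2.1). 1 year = 365.25 days (SAP 20.1.1.10), so the cut is 2 × 365.25 = 730.5 days. Planned N about 290 (SAP 5.2).

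**Assumed, because the documents are silent.** The share of partial onset dates and the distribution of disease duration.

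**1. The SAP's own examples.** Coding the rule returns 2016-Mar → 2016-03-01 and 2016 → 2016-01-01, as printed in 20.1.3.3.

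**2. Direction.** The imputed onset is never later than the true onset and Visit 1 is fixed, so imputed duration ≥ true duration. To confirm this, every Visit 1 date in 2017 (assumed year) was paired with every onset day in the preceding 2190 days: 365 × 2190 = 799,350 pairs.

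| Missing part | ≤2 y moved to >2 y | >2 y moved to ≤2 y | Most days added |
|---|---|---|---|
| Day | 5,373 | 0 | 30 |
| Day and month | 66,430 | 0 | 365 |

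With onset uniform over time, the share of truly ≤2-year subjects with a partial date who are moved averages 2.0% (day missing) or 24.9% (year only).

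**3. Where the year-only error arises.** Let Visit 1 fall at fraction f of its year and onset at fraction u of the calendar year two years earlier. True duration is 2 + f − u; imputed duration is 2 + f, which exceeds 2 for any f above 0. The true value is ≤2 when u ≥ f, which has probability 1 − f and averages 0.50 over f.

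**4. Number of subjects, year-only dates.** Assume exponential durations with median m, and λ = ln 2 / m. The probability that a year-only subject is moved is the integral over f from 0 to 1 of [e^(−λ(1+f)) − e^(−2λ)], which equals (e^(−λ) − e^(−2λ))/λ − e^(−2λ).

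| Median | Probability | 290 × 10% × probability | 290 × 30% × probability | Truly ≤2 y |
|---|---|---|---|---|
| 1.5 y | 0.108 | 3.1 | 9.4 | 175 |
| 3 y | 0.079 | 2.3 | 6.9 | 107 |
| 5 y | 0.055 | 1.6 | 4.8 | 70 |

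That is about 2 to 9 subjects, or roughly 2% to 7% of the short-duration group, with none moving the other way.

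**5. Number of subjects, day missing only.** With 10% to 50% partial dates and 30% to 50% truly at ≤2 years (assumed): 290 × 0.10 × 0.30 × 0.020 = 0.2, and 290 × 0.50 × 0.50 × 0.020 = 1.5. So about 0 to 2 subjects.

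**6. Onset before injury.**
- Year only: Visit 1 2017-09-01, injury 2015-09-20, true onset 2015-10-10 (692 days, 1.89 y). Imputed onset is 2015-01-01 (974 days, 2.67 y). The subgroup changes, and onset falls 262 days before the injury.
- Day missing: Visit 1 2017-09-10, injury 2015-09-15, true onset 2015-09-25 (716 days, 1.96 y). Imputed onset is 2015-09-01 (740 days, 2.03 y). The subgroup changes, and onset falls 14 days before the injury.

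**7. Effect on a subgroup contrast.** In the worst row of step 4, the >2-year group is 290 − 175 = 115, enlarged by 9.4, so 9.4/124.4 = 7.6% of it is misplaced. If the true difference were a step of 1 NRS point at 2 years (assumption), it would shrink by about 0.08. With SD 2.5 (assumption), the 95% half-width for that difference is 1.96 × 2.5 × √(1/175 + 1/115) ≈ 0.6.

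**8. What an injury-date floor does.** Repeating step 4 by simulation, with complete injury dates a mean 0.15 years before onset (assumption), the count falls to about 0.4 to 2 subjects, still with none moved wrongly into the short group.

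**The case against.** The best reply is that little depends on this. Protocol 1.5 and 14.1.2 make every analysis exploratory, SAP 13.2 makes the secondary efficacy endpoints descriptive, and Protocol 8.1 already urges caution without a comparator. Step 7 puts the bias well inside sampling error. All of that stands, and it limits the weight of the point.

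It can also be said that the rule keeps the short-duration group free of subjects placed there on a guessed month, and that plain mid-year imputation would put errors in both groups. That is true, but the injury-date floor also keeps the short group clean, and it removes most of the errors in step 4.

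The share of year-only dates may be small: Protocol 12.2.3.1 requires the onset date, and vague recall may be concentrated in remote onsets, which exceed 2 years anyway. This is plausible but undocumented, and SAP 20.1.3.3 itself provides for a missing month.

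An onset before injury feeds no derived interval, since the three times are summarised separately; and if both dates are partial at the same level in the same period, they tie. So the ordering problem matters mainly through the subgroup.

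The link from 8.2.1 to the imputed duration is inferred. SAP 11.3.3 and 20.1.3.3 hold the only derivation of duration, but 8.2.1 does not cite them. That is a reason to state the link.

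Two stronger readings should be resisted. A reader might take the 50% in step 3 as the overall error rate, but it applies only to year-only onsets in one calendar year. A reader might also infer that a subgroup-by-visit model is needed. No objective in Protocol 1.2 or SAP 4 asks whether duration modifies the effect, and separate subgroup presentation is the stated plan.

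**Conclusion.** The point holds, with limited reach. As written, the rule can only lengthen CRPS duration, so errors in the 2-year split all run toward the longer group, and it can contradict a recorded injury date. About 2 to 9 of 290 subjects would be affected if 10% to 30% of onsets are year-only and median duration is 1.5 to 5 years. About 0 to 2 would be affected if only the day is missing. These counts rest on assumed shares and an assumed exponential shape; the direction does not.

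The output affected is the subgroup presentation of the secondary efficacy endpoints and the CRPS-duration summary. A reader might infer that the efficacy results as a whole are biased. The documents do not support that: the overall summaries do not use duration, and the primary safety endpoint is untouched.

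**What to change.** In SAP 8.2.1, state that the subgroup uses duration from symptom onset to Visit 1 with the 365.25-day year, and restore the 2 in the second subgroup.

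In SAP 20.1.3.3, add a rule for this variable:
- Set the imputed onset no earlier than the precipitating-event date, and no later than the earlier of the diagnosis date and Visit 1, where those dates are known and more complete than the onset date.
- Where the precipitating event is unknown, which Protocol 12.2.3.1 allows, or the bounding dates are no more complete, use the recorded year or month, capped at Visit 1. The cap is needed because an uncapped midpoint can fall after Visit 1.
- Within the remaining interval, take the midpoint, accepting that a few subjects may then be misclassified in either direction. At minimum, keep the present rule and add the injury-date floor.
- Flag subjects whose remaining interval straddles 2 years, report how many there are, and repeat the subgroup summary under the alternative classification.

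The cost is SAP wording and minor programming before database lock. No new data are needed.

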**20.1.3.4 Prior and concomitant medication or therapy**

Prior and concomitant medication is collected as of enrollment in the eCRF and described like that in the trial protocol. For the analysis, the definition as described in the following is used.

The following rules are used to define the categories “prior” and “concomitant” medication.

Prerequisite is a complete date/time of first dose of IMP (entered or imputed). For subjects not allocated to treatment, the date/time of first IMP is not defined, and no prior or concomitant status will be assigned to their medications or therapies.

Stop of medication or therapy Date/time	Condition	Category
Complete date/time is available	Stop date/time is earlier than date/time of first dose of IMP	Prior
Missing month	Year of stop date is earlier than year of first dose of IMP	Prior
Missing day	Month/year of stop date are earlier than month/year of first dose of IMP	Prior
Missing hours	Day/month/year of stop date are earlier than day/month/year of first dose of IMP	Prior
Missing minutes	Day/month/year/hours of stop date/time are earlier than day/month/year/hours of first dose of IMP	Prior
Otherwise		Concomitant

Medication ticked in the eCRF as “continuing” will be classified as concomitant.

The following rules are used to identify medications or therapies which started after last dose of IMP.

Prerequisite is a complete date/time of last dose of IMP (entered or imputed).

Start of medication or therapy date/time	Condition	Start after last dose of IMP
Complete date/time is available	Start date/time is later than date/time of last dose of IMP	Yes
Complete date is available	Start date is later than or equal to date of last dose of IMP	Yes
Missing month	Year of start date is later than year of last dose of IMP	Yes
Missing day	Month/year of start date are later than month/year of last dose of IMP	Yes
Missing hours	Day/month/year of start date are later than day/month/year of last dose of IMP	Yes
Missing minutes	Day/month/year/hours of start date/time are later than day/month/year/hours of last dose of IMP	Yes
Otherwise		No

#### **20.1.4 Efficacy analysis**

There are no trial-specific definitions for this trial.

#### **20.1.5 Analysis of pharmacokinetic and pharmacodynamic parameters**

There are no trial-specific definitions for this trial.

#### **20.1.6 Safety analysis**

##### **20.1.6.1 Adverse events**

[figure not shown]
The result of all imputation strategies (e.g., incomplete start dates of adverse events), combination of observations and new derived information (e.g., treatment-emergent flag) must be stored in the Analysis of Data Model (ADaM) data set.

#### **Handling of missing date information**

The term missing date/time refers to a completely missing date/time or to an incomplete date/time where parts are not available, e.g., missing hours.

If the number of adverse events with missing date information does not exceed 10% the following imputation strategy is applied.

Missing start and end date/times will be imputed conservatively, i.e., missing values will be imputed in such a way that the duration of the adverse event is considered with the longest possible duration and such that, whenever the adverse event may potentially start after first IMP administration, the adverse event will be handled as a TEAE.

I1-I4: imputation steps

C1-C4: checkpoints

Figure 2: Graphical overview about the imputation strategy

Further explanations on the flow chart:

The different steps of the displayed imputation strategy must be completed from the first to the last step. All procedures in each step must be completed in the order given.

- Imputation:

- I1: Impute with date/time of first IMP
- I2:
  - a) Impute with first calendar day and/or first calendar month.  
Imputation will be done based on the available partial information starting with month and then day. The respective first month and day will be chosen for imputation:

Missing date	Imputed date
2014-Mar	2014-Mar-01
2014	2014-Jan-01

- I2:
  - b) Impute with first hour and/or first minute.  
Imputation will be done based on the available partial information starting with hour and then minutes. The respective first hour of a day and first minute will be chosen for imputation. “00:00” will be considered as the first hour/ first minute per day.

Missing time	Imputed time
11:--	11:00
--:--	00:00

- I3: Impute with date/time of informed consent signed  
If signing of informed consent was not collected with time information set adverse event start time to 00:00.
- I4:
  - a) impute with last calendar day and/or calendar last month  
Imputation will be done based on the available partial information starting with month and then day. The respective last month and day will be chosen for imputation:

Missing date	Imputed data
2014-Mar	2014-Mar-31
2014	2014-Dec-31

For February, leap years must be taken into account when calculating the last day in February.

1.1. b: impute with last hour and/or last minute

Imputation will be done based on the available partial information starting with hour and then minutes. The respective last hour of a day and last minute will be chosen for imputation. “23:59” will be considered as the last hour/ last minute per day.

Missing time	Imputed time
11:--	11:59
--:--	23:59

- Checkpoints
  - C1: The decision must be taken based on the available information (date/time) before imputation.
  - C2: adverse event stop date before first IMP
- 1.2. 1) The decision must be taken based on the available information (date/time) before imputation.
  - 2) If the end date is completely missing (with or without the information that the adverse event was continuing), this will be considered as after first IMP.
  - 3) If no IMP was given, this will be treated as adverse event stop date before first IMP.
- C3: The decision must to be taken based on the available information (date/time) before imputation.
- C4: The decision must to be taken based on the available information (date/time) before imputation.

A replacement of missing year for adverse event start information is not foreseen. If needed, this will be considered on a case-by-case decision which must be documented together with the documentation of ADaM data sets.

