### **12.3.1 Adverse events**

Adverse events will be documented from the time of enrollment (i.e., the time the informed consent form is signed) up to the time of the last protocol scheduled contact, i.e., date of last visit/contact (can be a phone call, e.g., in case of withdrawal).

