## 8 ANALYSIS CONVENTIONS

### 8.1 General principles

If 2 or more of the population sets as defined in the SAP coincide, presentations will only be prepared for 1 population.

All presentations will be done overall, i.e., for the single treatment group neridronic acid 400 mg. The data collected and derived in the trial will be presented in subject data listings.

Data collected in this trial will be summarized according to their nature as follows:

- Continuous variables: number of non-missing observations, arithmetic mean, standard deviation, minimum and maximum values, median and quartiles. If there are less than 5 observations, descriptive statistics will be presented based on the rules specified in Section 20.1.1.2.
- Categorical variables: absolute and relative frequencies. If not defined otherwise, the percentage denominator will be the number of subjects still in the trial at the respective time point in the analyzed population.
- Time-to-event variables: number of subjects, number of subjects with event, number of censored subjects, first quartile, median, and third quartile including 95% confidence interval. For calculating the survival estimate confidence interval (CI) bounds, the log-log transformed estimate of CI bounds will be used. In addition, Kaplan-Meier estimates and plots will be provided with the respective number at risk and the Kaplan-Meier estimates at the relevant time points together with the median and its 95% CI. Censoring mechanisms will be described in the respective section.

Medical terms (e.g., prior and concomitant diseases, adverse events) will be coded via Medical Dictionary for Regulatory Activities (MedDRA), and medications will be coded according to World Health Organization Drug Dictionary (WHO-DD).

[Table 1](#) shows the use of analysis sets in different analyses as defined in Section 9.

Table 1: Use of analysis sets

	Enrolled Set	Allocated Set	SAF	FAS	TCS	PD Set
Subject disposition	X					
Discontinuations		X				
Protocol deviations			X			
Demographics			X			
Other baseline characteristics			X			
Subject medical history			X			
Previous and concomitant medication			X			
Exposure			X			
Compliance			X			
Primary safety endpoint			X			
Secondary safety endpoint			X			
Secondary efficacy endpoints				X	X	
Adverse events			X			
Laboratory values			X			
Vital signs			X			
Twelve-lead ECG			X			
Physical examination			X			
Bone turnover markers						X
Health economics data				X		

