Denominator for percentage calculation will be the number of all TEAEs for presentation overall SOCs, and the number of TEAEs per SOC or PT respectively, for the presentation per SOC or PT, respectively.

Measures of location and variation will be calculated for:

- Duration of TEAEs.
- Time to onset of TEAE.

In addition, the time to onset of TEAE will be summarized using time-to-event methods pooled over all TEAEs. Time will be days until onset. The time to onset will be censored at the End-of-Trial-Visit, or at the time point of discontinuation if not due to TEAE.

The following listings will be produced for all enrolled subjects:

- Deaths.
- Serious adverse events other than death.

- Adverse events leading to discontinuation from the trial.
- Adverse events leading to permanent discontinuation from IMP.

In addition, adverse events associated with acute phase reaction will be presented for the SAF in a separate subject data listing. Adverse events associated with acute phase reaction include the PTs *Acute Phase Reaction* in all cases. They also include the PTs *Arthralgia*, *Bone pain*, *Chills*, *Fatigue*, *Headache*, *Influenza Like Illness*, *Musculoskeletal Chest Pain*, *Musculoskeletal Pain*, *Myalgia*, *Pain*, *Pain In Extremity* and *Pyrexia*, but only if occurring in the first 3 days after first IMP intake and not lasting longer than 3 days.

For TEAEs associated with the acute phase reaction, the incidence, incidence rate, the number of events and the percentage of events (related to the total number of events) will be summarized by PT.

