### **Duration of adverse event**

Duration of adverse event will be calculated based on the imputed values for adverse event start date/time and stop date/time.

If duration of adverse event could not be calculated due to unknown date information, the following assessment to categories will be used:

- If the adverse event is marked as “continuing” in the eCRF, the duration will be categorized as “continuing”

- Otherwise the duration category will be set to “missing”.

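### The printed rule for partial adverse-event end dates states no cap at death or at the last information on the event, so it can give durations longer than possible

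*SAP*

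**What the plan says.** SAP 20.1.6.1 (Handling of missing date information) sets the principle that "missing values will be imputed in such a way that the duration of the adverse event is considered with the longest possible duration". For end dates, step I4a is to "impute with last calendar day and/or calendar last month"; its examples turn March 2014 into 31 March 2014 and a bare 2014 into 31 December 2014. For a missing end time, "The respective last hour of a day and last minute will be chosen for imputation", that is, 23:59.

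The strategy is conditional: "If the number of adverse events with missing date information does not exceed 10% the following imputation strategy is applied". No rule is printed for a higher share.

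The other steps use the first IMP date (I1), the first calendar day or hour (I2) and informed consent (I3). No printed step brings in last contact, later follow-up information or death. Under List of deaths, death is identified only by a fatal outcome and is not tied to any end date.

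The imputed values reach a reported table. "Duration of adverse event will be calculated based on the imputed values for adverse event start date/time and stop date/time" (SAP 20.1.6.1, Duration of adverse event). SAP 15.1.1 then states that "Measures of location and variation will be calculated for" the duration of TEAEs. The standard set in SAP 8.1 is "Continuous variables: number of non-missing observations, arithmetic mean, standard deviation, minimum and maximum values, median and quartiles". Protocol 12.3.1 documents events "up to the time of the last protocol scheduled contact", and also has them followed until resolved or stable.

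**The concern.** An event recorded as ended cannot have ended after the subject's death, or after the last information anyone had about it. A calendar fill that ignores both dates can pass the maximum that the SAP's own principle aims for. It is then not a conservative value but an impossible one.

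The asymmetry is visible in the steps themselves: I1 and I3 use dates from the subject's own record, while I4 uses the calendar alone.

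At stake is the descriptive table of TEAE duration. Protocol 8.2 describes acute phase symptoms, the most common side effects of the class, as usually resolving in one to two days. Against durations that short, a single fill to 31 December is conspicuous in the mean, SD and maximum. A safety report could also list an event that ends after the subject's death.

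**Working it through.** **1. The plan's own examples.** Taking the last day of the known month, or 31 December if only the year is known, gives 31 March 2014 and 31 December 2014. Both match the SAP.

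**2. Can the rule pass the possible maximum?** Assumed dates: onset 20 February 2017; death, or last information on the event, 5 March 2017. Excess = imputed end − last possible end.

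- Month known: 31 March − 5 March = 26 days too long.
- Year only: 31 December − 5 March = 301 days too long.

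Counting first and last day, these are durations of 40 and 315 days against a maximum of 14.

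**3. Effect on the summary statistics.** Assumed: 20 events, 19 of them lasting 2 days, and one with onset 10 February 2018, end recorded as 2018, and last information 15 March 2018. Durations are date differences.

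- Rule: 10 February to 31 December = 324 days. Mean = (19 × 2 + 324)/20 = 18.1 days.
- Capped: 10 February to 15 March = 33 days. Mean = (19 × 2 + 33)/20 = 3.55 days.
- Excess: 324 − 33 = 291 days.
- SD, which here equals (x − 2)/√20 for a single long value x: 322/4.472 = 72.0 days against 31/4.472 = 6.9 days.
- Median: 2 days both times.

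In a pooled summary of 1,000 TEAEs (assumed), the same event moves the mean by 291/1000 = 0.29 days.

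**4. How much of the upward shift is due to the missing cap?** A simulation used 100,000 events per scenario. Its assumptions are not in the documents: entry uniform over one year, true duration exponential with mean 14 days, and every event ended by last contact. Overshoot = imputed end − true end. It averages about 14.7 days with the day missing and about 182 days with month and day missing. Ranges below run over two assumed onset patterns (first 10 days, or spread over follow-up).

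| Follow-up (days) | Day missing: past last contact | Day missing: removed by cap (days) | Month missing: past last contact | Month missing: removed by cap (days) |
|---|---|---|---|---|
| 365 | 0–7.5% | 0–1.0 | 5–53% | 0.8–67 |
| 182 | 0–15% | 0–1.9 | 55–78% | 56–116 |
| 60 | 7–45% | 0.7–5.8 | 88–95% | 144–164 |
| 14 | 88–91% | 12.5–13.1 | 99% | 180 |

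The impossible values concentrate in subjects with short follow-up. With a full year, most of the overshoot usually remains after capping.

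**5. Limit set by the 10% condition.** If a full 10% of events had partial end dates, the pooled mean would rise by 0.1 × 14.7 ≈ 1.5 days (day missing) or 0.1 × 182 ≈ 18 days (month missing). The largest single overshoots are 30 and 364 days (non-leap year), so the upper bounds are 3.0 and 36.4 days. These figures are the total effect of the rule, not the part due to the missing cap.

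**The case against.** The strongest reply is that the notes explain a flow chart that cannot be seen. For checkpoints C3 and C4 the notes say only that decisions use the information available before imputation; the conditions themselves are not visible. A reader might infer that the plan certainly has no cap. The documents support only the narrower statement that none is printed. Still, all four imputation steps are written out, and none supplies a date of death or last contact.

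Second, a reader might infer that the missing cap is why mean duration is too long, or that such events will dominate the tables. That is not supported. The upward direction is a declared choice, most of it would usually survive a cap in fully followed subjects, and the number of affected events is unknown. The 20-event example needs a year-only end date, an early leaver and a small group. SAP 15.1.1 does not say that duration is summarised by event type.

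Third, there are safeguards: the 10% condition, the median and quartiles, the categories for durations that cannot be calculated, and storage of imputed values in the analysis data sets. These limit how many events are affected and make them traceable. They do not limit how far one date can overshoot.

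Fourth, an end after the last scheduled visit is not in itself impossible, because Protocol 12.3.1 has events followed to resolution. This stands, and the cap must allow for it.

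**Conclusion.** The point holds as a minor one. As printed, I4 can place an end date after death or after the last information on an ended event, and so exceed the SAP's own maximum-duration principle. The mean, SD and maximum of TEAE duration can be inflated, chiefly through subjects who die or leave early. The actual size cannot be known without the number of partial end dates; the figures above rest on the stated assumptions and on Figure 2 holding no cap.

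A reader might infer that the main safety result is affected. It is not: the primary endpoint is the occurrence of any TEAE, time to onset runs from first IMP to the start date, checkpoint C2 uses stop-date information before imputation, and no inferential testing is planned. The median is little affected.

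**What to change.** Add to step I4:

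> The imputed end date/time is the earliest of the calendar imputation, the date of death, and the later of the date of last contact and the last available follow-up information on the event. The cap is not applied where it would contradict the recorded part of the end date or fall before the event start.

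The second sentence is needed. With an end recorded as April 2018 and last contact on 15 March, an unguarded cap would move the event out of its recorded month. Report the number of imputed and of capped end dates beside the duration table, and check Figure 2 for consistency.

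The cost is small but not nil: some extra derivation and checking. The date of last follow-up information is not among the adverse-event items listed in Protocol 12.3.1 and may not be held for each event; where it is not, use the last contact date. The cap does not remove the upward shift that comes from the declared rule itself.
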